**Phosphodiesterase Type 5 Inhibition to Improve
Endothelial Function and Vascular Remodeling in
Chronic Kidney Disease and End Stage Renal Disease
Patients Requiring New Arteriovenous Fistula
Study Protocol and Statistical Analysis Plan**

NCT Number: NCT02414204

July 11, 2018

[name], Principal Investigator
University of Alabama at Birmingham
Birmingham, AL 35294

“Phosphodiesterase Type 5 Inhibition to Improve Endothelial Function and Vascular Remodeling in Chronic Kidney Disease and End Stage Renal Disease Patients Requiring New Arteriovenous Fistula”.

PI: [name]., M.S.P.H, F.A.C.P., F.A.S.N.
Associate Professor of Medicine
Department of Medicine/ Division of Nephrology
Mailing address: [name]
[contact]
[contact]
Email: [contact]

Protocol Version: 1.0

Protocol Date: 2-5-15

Protocol

1. Background:

The vascular access is the “Achilles Heel” of the hemodialysis procedure. 60% of arteriovenous fistulas (AVFs) created fail to mature adequately for hemodialysis (AVF non-maturation), due to a combination of early aggressive venous neointimal hyperplasia development and inadequate vasodilation (adverse remodeling). At present, there are no effective therapies to treat vascular access dysfunction. The treatment paradigms to date have focused on delivery of therapies post-AVF creation and most recently at the time of surgery. Preliminary data from the Hemodialysis Fistula Maturation (HFM) consortium suggests that profound endothelial dysfunction, as measured by flow-mediated (FMD) and nitroglycerin-mediated (NMD) in the brachial artery, is present in the large majority of patients prior to AVF creation. This suggests that the vascular health of the vessels at the time of AVF creation may play an important role in AVF non-maturation. Furthermore, the period immediately after AVF creation is important because the blood vessels are adjusting to new hemodynamic parameters. There are no previously published studies addressing therapies to modify or improve endothelial function prior to and after vascular access creation. Sildenafil, a phosphodiesterase 5 inhibitor that enhances the effects of nitric oxide (NO), has been shown in experimental and clinical studies in cardiovascular disease to improve endothelial function and decrease vascular stenosis. Therapies to enhance endothelial function, through NO production, have not been evaluated in vascular access dysfunction to date and may be beneficial in AVF maturation.

2. Recruitment Population:

Patients with stage IV and V chronic kidney disease and end stage renal disease requiring hemodialysis at UAB Dialysis Clinics will be recruited from the UAB Vascular Access Clinic, which has been the site for recruitment of patients requiring new vascular access for the last 10 years.

3. Inclusion/Exclusion Criteria:

Inclusion Criteria:

1. Age ≥ 19 years of age male or female
2. Chronic Kidney Disease Stage IV or V patients or End Stage Renal Disease Patient requiring arteriovenous fistula surgery

Exclusion Criteria:

1. Patient currently on nitrate therapy or any nitric oxide donor in any form
2. Patient currently on protease inhibitor or non-nucleoside reverse transcriptase inhibitor
3. Patient with resting systolic blood pressure < 90 mm Hg and diastolic blood pressure < 50 mm Hg.
4. Patient life expectancy < 9 months.
5. Patient unable or unwilling to meet study requirements.

4. Randomization Process:

Sildenafil will be purchased and obtained by the UAB pharmacy. The pharmacy will over-encapsulate the Sildenafil tablets to match a placebo encapsulated tablet.

The first subject recruited will be unblinded and receive Sildenafil. After the first subject, all subsequent subjects will begin the randomization process.

Randomization Process: Subjects agreeing to this study will be randomized at the 1st vascular function testing visit. 20 numbers generated by a biostatistician will be randomly assigned numbers to the Sildenafil treatment group (10 numbers) and randomly assigned to the placebo (10 numbers). The investigators and clinical coordinators will be unblinded to the treatment group of the subject and have access to the randomization assignments.

1. Treatment/Intervention Group: 10 patients will take Sildenafil 20 mg twice a day oral from the time after randomization (1st vascular test visit) until the 2 weeks post-operative arteriovenous fistula ultrasound.

2. Placebo Group: 10 patients will take placebo twice a day oral from the time after randomization (1st vascular test visit) until the 2 weeks post-operative arteriovenous fistula ultrasound.

5. Procedures and Study Visits:

Study Procedures:

Randomization will occur at the time of the 1st vascular function testing. The first subject will be unrandomized and receive Sildenafil. Subsequent subjects will be randomized to receive either

Sildenafil 20mg twice a day or placebo twice a day, based on randomization scheme. Subjects will begin either placebo or Sildenafil after randomization during the first vascular function visit until the 2 weeks postoperative arteriovenous fistula ultrasound.

Enrolled subjects will have an initial brachial artery flow-mediated dilation (FMD) and venous plethysmography (VP) studies performed approximately 2 weeks prior to scheduled AVF creation and a subsequent FMD and VP study prior to surgery. The FMD and VP studies are non-invasive studies. Completion of these studies will take approximately 3-4 hours.

Up to four teaspoons of blood will be drawn at the 1st FMD/VP study prior and second FMD/VP study. Blood samples will be obtained using the standard method used to obtain blood for routine hospital tests. Completion of blood draw will take approximately 10-15 minutes.

Pre-operative, 2 weeks and 6 weeks post-operative ultrasounds will be performed on participants. The pre-operative and 6 week ultrasounds are part of standard medical care and will be performed whether the participant is in the study or not.

Discarded vein and artery specimens (approximately 5-10 mm each) will be collected at the time of AVF surgery. This procedure requires 3-5 minutes, and does not affect surgical outcome.

A total of 21 subjects will be recruited for this study with prospective follow-up. The first patient will be unblinded and receive the drug. Subsequently, 10 subjects will be randomized to receive 20 mg of Sildenafil twice a day oral and 10 patients randomized to receive placebo twice a day oral. Information related to demographics, comorbidities, and AVF outcome following surgery will be collected. The primary clinical endpoint is change in baseline and 2 week FMD/VP measurements. The secondary outcome is change in blood flow and vein and artery diameters at 2 and 6 weeks.

Study Visits:

Visit 1: Screening and enrollment 1-2 hours (Research)

- Informed consent
- The study team will determine qualification to participate in this study

Visit 2: Baseline Visit (in some cases Visit 1 and 2 could be combined) (Research)

- Detailed medical history
- Height and weight measured
- Blood draw (in some cases this could occur in the dialysis unit)

Visit 3: 1st Vascular Function Test and Pre-operative Ultrasound

- Vascular Ultrasound (Standard care)
- Vascular Function Testing (3-4 hours)
 - Brachial artery flow mediated vasodilation and venous plethysmography (Research)
- Blood draw (if not collected during visit 2) (Research)
- Randomization to either study drug Sildenafil or placebo

Visit 4: 2nd Vascular Function Test

- Vascular Function Testing (3-4 hours)
 - Brachial artery flow mediated vasodilation and venous plethysmography (Research)

Visit 5: Arteriovenous Fistula Surgery

- Fistula creation (Standard care)
- Discarded vein and artery tissue collection (Research)

Visit 6: 2 Weeks Post-Operative Ultrasound

- Vascular Ultrasound (Research)

Procedures and Length of Time:

Procedure	Length of Time Required of Participants	Frequency of Repetition	Research (Res) – OR- Routine Care
Blood Drawing	10-15 minutes	Baseline Visit Week 2	 Res  Routine  Res  Routine
Height and Weight	5 minutes	Baseline visit	 Res  Routine
Taking Sildenafil 20 mg or Placebo bid oral	2 minutes	Daily from the time after randomization (1st vascular test visit) until the 2 weeks post-operative arteriovenous fistula ultrasound	 Res  Routine
Vascular Function Testing –FMD and VP	3-4hrs	Pre-operatively at baseline Two weeks after baseline	 Res  Routine  Res  Routine
Vascular Ultrasound	1-2hrs	Pre-operative Week 2 Visit Week 6 Visit	 Res  Routine  Res  Routine  Res  Routine

Discarded Vein and Artery Tissue Collection	3-5 minutes of surgery time	Once	 Res  Routine

6. Length of Time of Follow-up and Subject Participation:

Total Follow-up Time: 2 years to follow clinical data related to clinical survival of the fistula.

Total Participant Time: Up until the six week postoperative ultrasound.

**Phosphodiesterase Type 5 Inhibition to Improve
Endothelial Function and Vascular Remodeling in
Chronic Kidney Disease and End Stage Renal Disease
Patients Requiring New Arteriovenous Fistula**

Statistical Analysis Plan

NCT Number: NCT02414204

July 11, 2018

[name], Principal Investigator
University of Alabama at Birmingham
Birmingham, AL 35294

The data will be analyzed in two stages: (1) descriptive statistics, which will include means and standard deviations for normally distributed continuous variables, medians and interquartile ranges for skewed continuous variables, and proportions for categorical measures and (2) two-group t test, Wilcoxon rank-sum tests, chi-square tests, and simple logistic regression and multiple logistic regression modeling. P values <0.05 will be considered statistically significant.

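### Exclusion 3 joins its two blood-pressure limits with *and*, so as written a patient below only one of them can be enrolled

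*Combined protocol and SAP*

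**What the plan says.** The eligibility rules are in protocol section 3. There are two inclusion criteria (age, and kidney disease needing fistula surgery) and five exclusions. The third exclusion is the only one about blood pressure: "Patient with resting systolic blood pressure < 90 mm Hg and diastolic blood pressure < 50 mm Hg".

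The other four concern nitrates and nitric oxide donors, certain antiretroviral drugs, life expectancy, and ability or willingness to take part.

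On exposure, section 5 says of the first subject: "The first patient will be unblinded and receive the drug". After that, "10 subjects will be randomized to receive 20 mg of Sildenafil twice a day oral" and another 10 receive placebo, which makes 21 in all. Section 4 sets the dosing period, which runs "from the time after randomization (1st vascular test visit) until the 2 weeks post-operative arteriovenous fistula ultrasound". Section 5 places the first vascular test by saying it is "performed approximately 2 weeks prior to scheduled AVF creation".

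**The concern.** A blood-pressure exclusion with two limits is normally meant to work limit by limit: a patient who falls below either one stays out. Joined by *and*, neither limit works on its own. The systolic limit has no effect unless the diastolic reading is also below 50 mm Hg, and the diastolic limit has none unless the systolic reading is also below 90 mm Hg.

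What is at stake is participant safety, not the analysis. The Background (section 1) describes the study drug as enhancing the effect of nitric oxide, and the protocol itself chose to set a blood-pressure floor for entry. The documents do not say that this dose lowers blood pressure. That a patient with low pressure is a poor candidate for it is a clinical inference, although having the exclusion at all suggests the authors shared it. Dosing also spans fistula surgery and the two weeks after it, when, as the Background notes, the vessels are adapting to changed haemodynamics.

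**Working it through.** **1. What the criterion does as written.** There are four possible combinations of the two readings:

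| Systolic < 90 | Diastolic < 50 | Example (mm Hg) | As written (*and*) | With *or* |
|---|---|---|---|---|
| yes | yes | 85/45 | excluded | excluded |
| yes | no | 80/55 | eligible | excluded |
| no | yes | 95/45 | eligible | excluded |
| no | no | 120/70 | eligible | eligible |

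The wording in force excludes one combination of four. The *or* form excludes three.

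**2. Whether the list's own usage suggests another reading.** Where either of two conditions is meant to suffice, the same list uses *or*. Exclusion 1 reads "Patient currently on nitrate therapy or any nitric oxide donor in any form" and exclusion 2 reads "Patient currently on protease inhibitor or non-nucleoside reverse transcriptase inhibitor". Exclusion 5 is built the same way. A coordinator who reads the list consistently has reason to take the *and* in exclusion 3 at face value.

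**3. Whether anything else closes the gap.** None of the other exclusions, and neither inclusion criterion, refers to blood pressure. Visit 1 (section 5) leaves it to the study team to decide who qualifies, which leads back to these same criteria. The visit list and the procedures table name height, weight, blood draws, vascular testing, ultrasound and tissue collection, but no blood-pressure measurement. No rule for stopping or reducing the dose because of low pressure is given. Exclusion 3 is therefore the only written blood-pressure safeguard.

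**4. Planned exposure.**
- Subjects on sildenafil: 10 randomized + 1 first, open subject = 11. Share: 11/21 = 0.524, or 52%.
- Duration: about 14 days before surgery + 14 days after = about 28 days.
- Doses per subject: 28 × 2 = about 56.

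These figures describe everyone on sildenafil. They show what an admitted patient would receive, not how often the wording would matter.

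**5. Scale of the gap, under assumption.** The documents give no blood-pressure distribution. Let p be the assumed share of otherwise eligible patients who are below exactly one limit, and suppose the wording is applied literally. Among the 11 on sildenafil, the expected number is 11p and the chance of at least one is 1 − (1 − p)^11.

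| Assumed p | 11p | 1 − (1 − p)^11 |
|---|---|---|
| 1% | 0.11 | 0.105 |
| 5% | 0.55 | 0.431 |
| 10% | 1.1 | 0.686 |

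The plan states no figure of its own on this point, so there is none to reproduce.

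**The case against.** The strongest reply is that intent is unknown. If the *and* is loose drafting for two separate limits, the study team that wrote it may already apply it as *or*, and this is only a clarification. If it is a deliberate joint threshold, nothing in the documents shows that a patient below one limit is at unacceptable risk, and prescribing *or* is a preference. There are also practical protections: recruitment is from one vascular access clinic, the study team judges eligibility, and section 4 leaves investigators and coordinators unblinded, so they know who takes sildenafil. Finally, the probabilities above only restate assumed inputs.

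Some of this stands. The documents do not settle intent, the clinical risk is inferred and not stated, and the probabilities carry no more information than the assumed shares. Clinical judgement does make it less likely that a plainly hypotensive patient would be enrolled.

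The objection does not rescue the wording, though. If *or* was meant, the text is wrong and eligibility depends on who reads it. If *and* was meant, the documents give no reason for admitting a patient with a systolic pressure of 80. Clinical judgement and knowledge of the assignment are not a written rule.

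**Conclusion.** The concern holds as stated. Followed literally, exclusion 3 admits patients who are below one of its own two limits, and nothing else in the protocol or SAP keeps them out. The finding rests on the text alone and does not depend on the assumed shares.

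Its practical size cannot be determined from the documents. Over assumed shares of 1% to 10%, between 0.11 and 1.1 such patients would be expected among the 11 on sildenafil, and none at all is possible. Those figures also assume literal application at every enrolment. The point should be corrected because it concerns participant safety and is cheap to close. It does not affect randomization, the endpoints, the planned sample size or the analysis, and there is no claim here that anyone was harmed. Confidence is medium, because the authors' intent is not shown.

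**What to change.** In protocol section 3, exclusion 3, replace *and* with *or*, so that a resting systolic pressure below 90 mm Hg or a resting diastolic pressure below 50 mm Hg is each enough to exclude. The same amendment could usefully name the visit at which resting pressure is taken, since the visit schedule lists no such measurement.

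The cost of the wording change is a one-word amendment and the loss of patients below exactly one limit. With the same assumed shares, filling 21 places would need 21/(1 − p) otherwise eligible patients: 21.2, 22.1 or 23.3 at 1%, 5% or 10%, that is, about 0.2 to 2.3 more. The endpoints, visits, planned sample size and analysis stay as they are. If the joint threshold was deliberate, the protocol should instead say so and justify enrolling patients below one limit.

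### Dialysed and non-dialysed patients share one unstratified list, vascular tests are not tied to the dialysis cycle, and no linear model can adjust the change: a cost in precision and conditional bias, not inflated type I error

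*Combined protocol and SAP*

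**What the plan says.** **Who is enrolled.** Inclusion criterion 2 (protocol section 3) admits "Chronic Kidney Disease Stage IV or V patients or End Stage Renal Disease Patient requiring arteriovenous fistula surgery". Section 2 describes the source as "Patients with stage IV and V chronic kidney disease and end stage renal disease requiring hemodialysis at UAB Dialysis Clinics". No quota or expected share on dialysis is given.

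**Allocation.** Section 4 describes a single list: "20 numbers generated by a biostatistician will be randomly assigned numbers to the Sildenafil treatment group (10 numbers", with the other 10 going to placebo. It mentions no strata, blocks or minimisation. Section 5 gives the total: "A total of 21 subjects will be recruited for this study with prospective follow-up". That is 10 + 10 randomised, plus a first subject who receives sildenafil without randomisation.

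**Endpoint and timing.** Section 5 states: "The primary clinical endpoint is change in baseline and 2 week FMD/VP measurements". The first test is "performed approximately 2 weeks prior to scheduled AVF creation and a subsequent FMD and VP study prior to surgery". The procedures table places the second test two weeks after baseline. Neither test is placed relative to a dialysis session. Within the visit list, the dialysis setting appears only as a possible place for blood sampling: "Blood draw (in some cases this could occur in the dialysis unit". The only listed measure that bears on fluid state is at Visit 2: "Height and weight measured". No weight is listed at either vascular test.

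**Analysis.** The SAP lists a two-group t test, rank-sum and chi-square tests, and simple and multiple logistic regression. It names no covariates and no linear model for a continuous outcome.

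**The concern.** Dialysis status is known before randomisation and could plausibly affect how vascular measurements move over two weeks. Dialysed patients have fluid removed between the tests. The others do not, unless they start dialysis in that interval. A dialysed subject tested before a session at one visit and after it at the other may show a change that has nothing to do with the drug.

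Two consequences need to be kept apart:

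- **Lost precision.** Unmatched test timing adds variance to the change score of dialysed subjects. With 10 per arm there is little precision to spare.
- **Conditional bias.** If the mean change differs between dialysed and non-dialysed subjects, and the arms differ in their dialysed share, the difference between arms contains a part that is not a drug effect. The listed two-group tests do not remove it. Logistic regression, the only multivariable method listed, does not fit a continuous change.

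**Working it through.** **The plan's own figure.** 1 + 10 + 10 = 21, as stated. The documents give no effect size, SD or power, so the sample size cannot be derived further. The calculations below concern the 20 randomised subjects.

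**Inputs.** From the documents: 20 randomised, 10 per arm, one unstratified list, a change score as endpoint, significance at 0.05 (two-sided assumed). Assumptions: the number K of 20 on dialysis, the difference d in mean change between dialysed and non-dialysed subjects, and the ratio r of their SDs. The unit is the within-stratum SD of the change.

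**1. Chance of imbalance.** The dialysed count in one arm is hypergeometric. For K = 10:

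P(7 v 3 or worse) = 2 × (14400 + 2025 + 100 + 1) / 184756 = 33052/184756 = 17.9%.

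| K on dialysis | P(arms differ by 4 or more dialysed subjects) |
|---|---|
| 4 | 16016/184756 = 8.7% |
| 6 or 14 | 26026/184756 = 14.1% |
| 8 or 12 | 31372/184756 = 17.0% |
| 10 | 33052/184756 = 17.9% |

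For K = 10, a split of 8 v 2 or worse has a chance of 2.3%.

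**2. Shift in the treatment difference at 7 v 3, with no drug effect.** Shift = (0.7 − 0.3) × d. The standard error must include the spread that the same dialysis effect creates within each arm: variance = 1 + d² × 0.7 × 0.3 × 10/9, and SE = √(variance × 2/10).

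- d = 0.5: shift 0.20 SD; variance 1.058; SE 0.460; shift/SE = 0.43.
- d = 1.0: shift 0.40 SD; variance 1.233; SE 0.497; shift/SE = 0.81.

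**3. False-positive rate of the unadjusted t test** (simulation, K = 10, 100,000 runs per scenario).

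| d | 5 v 5 | 7 v 3 | 8 v 2 | All allocations |
|---|---|---|---|---|
| 0.5 | 4.4% | 6.4% | 9.0% | 5.1% |
| 1.0 | 2.9% | 9.4% | 19.9% | 5.1% |

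Over all allocations the test keeps its level. It is conservative in balanced lists and liberal in unbalanced ones.

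**4. Adjustment for dialysis status in a linear model.** For d = 1.0 and an imbalance of 4 or more, the false-positive rate is 4.9%. The SE over all allocations, unadjusted, follows from √{0.2 × (1 + d² × 5/19)}: 0.503 for d = 1.0 and 0.462 for d = 0.5. The adjusted SE is about 0.46 whatever d is. So adjustment gains precision at d = 1.0 (0.50 to 0.46) and breaks even near d = 0.5. It costs a little if d = 0, where the unadjusted SE is √(2/10) = 0.447.

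**5. Timing noise alone.** Suppose mismatched timing makes the SD in dialysed subjects r times that of the others, with no mean shift. At 7 v 3 the simulated false-positive rate is 5.0%, 5.0% and 4.8% for r = 1.5, 2 and 3, so there is no material inflation. The SE of the treatment difference, with 10 dialysed among 20, is √{(10r² + 10)/100}: 0.57, 0.71 and 1.00, against 0.447 at r = 1. This route costs precision only.

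**6. How much precision there is.** With 10 per arm and no added noise, 80% power needs a true difference of 1.32 SD. Power at 1.0 SD is 56%.

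**The case against.** The strongest case against the point is this. Randomisation already covers chance imbalance, and the 5% level holds over all lists. The endpoint is a within-patient change, so stable differences in level between dialysed and non-dialysed patients largely cancel. Nothing in the documents says that the two-week change differs by dialysis status. A nominal 14-day gap would bring a patient on a weekly dialysis timetable (assumption) back to about the same point in the cycle. Whether to stratify a list of 20 is a matter of choice.

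Most of this stands, and it sets the limits of the point. Three parts do not remove it. Only one allocation will be realised, and the SAP names no analysis of the continuous change that could correct an unbalanced one. The 14-day gap is no guarantee, because section 5 gives the lead time to surgery as approximate and places the second test simply before surgery. And fluid state can differ between the two tests, so it does not cancel in the change score.

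Two stronger readings are tempting:

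- **That the design makes a false drug effect more likely overall.** It does not: step 3 gives about 5% over all allocations, and step 5 shows that random timing mismatch adds variance, not a mean shift.
- **That test timing will differ systematically between arms, because section 4 leaves investigators and coordinators unblinded.** The route is open, but nothing in the documents says that bookings depend on allocation. A fixed interval would close that route in any case.

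**Conclusion.** The point holds as a modest one about precision and conditional bias; correcting it is desirable rather than essential. Three features are on the page: a mixed population on one unstratified list, vascular tests not tied to dialysis, and no linear model for the continuous change.

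The size rests on assumptions. The dialysed share is not given, and a difference of 4 or more between arms has a chance of 9-18% for 4 to 14 of 20 on dialysis. The effect of dialysis status on the mean change is also unknown. If it is zero there is no bias, and if it is 0.5-1.0 SD the figures in steps 2 and 3 apply at a 7 v 3 split. Confidence in the three facts is high; confidence in the magnitude is low. The case for matching test times does not depend on any mean shift, since it removes noise whichever way the mismatches fall.

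**What to change.** 1. **Section 5, visits.** For dialysed subjects, book Visits 3 and 4 at the same interval from the last dialysis session. For all subjects, record weight at each test and any start of dialysis between the tests; for dialysed subjects, record the interval as well. Cost: less flexible booking; no extra staff or procedure beyond a weight.

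2. **SAP.** Analyse the FMD and venous plethysmography changes with a linear model containing arm, baseline value and dialysis status at Visit 3, and report dialysis status by arm. Cost: one degree of freedom for each of the two covariates, and a slight loss of precision if dialysis status turns out not to matter (step 4). This needs no new list, and the covariate should be available from the detailed medical history at Visit 2.

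3. **Section 4, optional.** If the list is not yet in use, generate it in two strata (on dialysis or not at Visit 3) with small blocks. Cost: arm sizes may differ slightly from 10:10 if the strata fill unevenly. This is the most debatable of the three, and item 2 already deals with most of the conditional bias.

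### Investigators and coordinators are unblinded and can see the randomization assignments, with no protected list and no masked assessor required for the primary FMD/VP endpoint

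*Combined protocol and SAP*

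**What the plan says.** Section 4 (Randomization Process) describes 20 numbers generated by a biostatistician, 10 for sildenafil and 10 for placebo, and then states: "The investigators and clinical coordinators will be unblinded to the treatment group of the subject and have access to the randomization assignments". The same section says of the product: "The pharmacy will over-encapsulate the Sildenafil tablets to match a placebo encapsulated tablet". It treats one subject separately: "The first subject recruited will be unblinded and receive Sildenafil".

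Section 5 (Procedures and Study Visits) gives the eligibility decision at Visit 1 to the people running the trial: "The study team will determine qualification to participate in this study". At Visit 3 the last item, after the ultrasound, vascular function testing and any outstanding blood draw, is "Randomization to either study drug Sildenafil or placebo". The endpoint is set in the same section: "The primary clinical endpoint is change in baseline and 2 week FMD/VP measurements".

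Neither document says who performs or reads FMD, VP or the ultrasounds, or whether that person is masked. The SAP does not mention blinding.

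**The concern.** Two separate protections are missing.

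- **Allocation concealment.** Staff who recruit and judge eligibility may know the next assignment. They could then influence who enters, and when, according to the arm that is coming.
- **Masked measurement.** A person who knows the arm may acquire or read the second FMD/VP study differently by arm, even without meaning to.

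Either route would produce a difference between arms that is not due to sildenafil. The t test and Wilcoxon test listed in the SAP compare the arms as recorded, so they cannot separate such bias from a drug effect. With 10 per arm, a few selected enrolments or shifted readings could matter.

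**Working it through.** The plan gives no power calculation, effect size, SD or assessor error, so there is no stated figure to reproduce. The head count is consistent: 1 + 10 + 10 = 21.

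**Step 1: is the list protected?** Section 4 gives access to the assignments and sets no time limit on it. It describes no pharmacy-held list, envelopes or central release. The visit order in section 5 places eligibility at Visit 1 and lists randomization after FMD/VP at Visit 3. That governs when a subject is assigned, not when staff may look at the list. Access only after each assignment would fit the wording, but is not required.

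**Step 2: how much room is there for selection?** Most criteria are objective. Judgement enters mainly through the life-expectancy exclusion, the exclusion worded "Patient unable or unwilling to meet study requirements", and the timing of enrolment.

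**Step 3: how predictable are the assignments?** The input is a fixed list of n = 20, split 10:10 (section 4).

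- Ordered list visible before enrolment: up to 20 of 20 known.
- List concealed, but each arm learned afterwards: the expected number of correct best guesses is n/2 + 2^(n−1)/C(n, n/2) − 1/2 = 10 + 524,288/184,756 − 0.5 = 10 + 2.84 − 0.5 = 12.34, or 62%.
- Staff blinded throughout: 10 of 20.

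**Step 4: how sensitive is the primary comparison to measurement bias?** This is an illustration only. It assumes no true effect, all 10 per arm analysed, a two-sided t test at 0.05 (the SAP gives 0.05 but not the sidedness), and a bias of d SDs of the measured change between arms. With 18 degrees of freedom and noncentrality δ = d × √(10/2) = 2.236d, the false-positive rate is P(|T| > t₀.₉₇₅,₁₈), where T is noncentral t with parameter δ.

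| Assumed bias d (SD) | δ | False-positive rate |
|---|---|---|
| 0 | 0 | 5.0% |
| 0.1 | 0.224 | 5.5% |
| 0.25 | 0.559 | 8.3% |
| 0.5 | 1.118 | 18.5% |
| 1.0 | 2.236 | 56.2% |

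A simulation of 100,000 trials per row gave 5.0%, 5.6%, 8.3%, 18.4% and 56.2%. At 0.1 SD the harm is negligible, and 1.0 SD is an extreme case. Nothing in the documents places this trial on that scale.

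**The case against.** The strongest defence is that this is a participant-blind trial by design. Matched capsules mask the subjects, staff know the arm, and the first subject is called unblinded because that person knows the drug is sildenafil. On that reading the text is coherent. Knowing the treatment group need not mean seeing the next assignment, and the visit order means that eligibility and baseline would normally come before it. Only investigators and coordinators are unblinded, and nothing says they perform or read FMD or VP. The bias sizes are assumed.

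Much of this stands as a limit on what can be claimed. The 20 of 20 figure is the worst case. On the post-assignment reading the gain is about two correct guesses (12.3 against 10), with limited discretion to act on them. A masked operator is possible. Bias is possible but not shown.

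It does not remove the concern. A coherent participant-blind design still lets staff who know the arm enrol subjects and, as far as the text goes, measure the primary endpoint. The plan gives no reason for accepting this when matched capsules are already being made.

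The opposite defence is that unblinded is a slip for blinded, since matching the capsules and singling out the first subject fit poorly with staff who know every arm. That does not rescue the sentence either: its second half would still give blinded staff access to the assignments.

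**Conclusion.** The concern holds. As written, the plan gives investigators and coordinators the assignments, does not protect the list before eligibility and baseline testing, and requires no masked acquisition or reading of the primary endpoint. This follows from the text and does not depend on the illustrative rates.

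The size of any resulting bias cannot be determined from the documents. Predictability runs from 12.3 to 20 of 20 assignments, depending on when staff gain access. The false-positive rate stays close to 5% if measurement bias is small and reaches 18.5% at an assumed 0.5 SD. The sentence must be corrected because concealment and masked measurement support the trial's only randomized comparison, and the planned analysis cannot restore them afterwards.

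**What to change.** The sponsor should first confirm whether staff were meant to be unblinded. Then replace the sentence in section 4 with text such as:

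> For the 20 randomized subjects, the randomization list is held only by the UAB pharmacy and the biostatistician who generated it. The pharmacy uses the next assignment for dispensing only after eligibility is recorded and the baseline FMD/VP study is complete. Investigators, coordinators and the existing staff who acquire or read FMD, VP and research ultrasound studies remain blinded until database lock, with emergency unblinding through the pharmacy.

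If staff have already seen the list, generate a new concealed sequence for the remaining subjects. It should not force the final totals to 10:10, because known past arms would then make the remaining assignments partly predictable; the price is a possible imbalance. Have any recordings that were kept read under coded IDs, and report who knew the assignments and when. If enrolment is already complete, which the documents do not state, only coded reading and disclosure can still help.

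The cost is a short protocol amendment. The pharmacy already prepares the matched capsules and a biostatistician already generates the numbers. The documents do not say that the pharmacy can hold the list and handle unblinding, so that must be confirmed. Coordinators would have to go through the pharmacy to unblind a subject.
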